## Data Safety Monitoring Committee

To be appointed.

## Consumer groups

To be appointed.

# TRIAL OF AN INDIVIDUALISED INTERVENTION FOR THE PREVENTION OF STROKE (TIIPS)

## BACKGROUND AND RATIONALE

### 1. THE IMPACT OF TIA/MINOR STROKE

Patients with Transient Ischaemic Attack (TIA) and minor (non-disabling; (NIHSS  $\leq$  3)[1] stroke are at high risk of secondary vascular events, including major stroke, myocardial infarction (MI), cognitive deficits and death, with population-based studies reporting incidence of adverse outcomes as high as 25% within 90 days.[2] New vascular events, including fatal strokes, MI, and other cardiovascular deaths, occur in up to 26% of patients within four years post-TIA.[3, 4] Increased risk is associated with an unhealthy lifestyle and poor adherence to medications to treat elevated blood pressure, diabetes mellitus, and previous vascular disease.[3] ARCOS-IV[5] showed that the age-standardised incidence of first-ever TIA in NZ is one of the highest among developed countries at 50 [95%CI 46-55] per 100,000 persons in 2011-2012.[6] TIA occurred at a younger mean age in Māori and Pacific people (60 years) and Asian and other (including Middle Eastern and African) people (68 years) compared to Europeans (74 years).[6] ARCOS-IV also found a high prevalence of cardiometabolic risk factors (e.g. 65% had hypertension, 47% had elevated lipids, and 27% had atrial fibrillation).

### 2. SECONDARY PREVENTION AFTER TIA/MINOR STROKE

There is ample evidence that modifying health behaviours for stroke and cardiovascular disease (CVD) prevention is feasible, improves health outcomes, reduces healthcare costs, can reduce individual risk of stroke by about 80%.[7][8] and can reduce stroke incidence by about 50%.[9] Addressing health behaviours, including the use of multifactorial lifestyle interventions,[10] can lead to clinically meaningful reductions in CVD and stroke.[11] Both TIA and minor stroke are highly preventable with medical management,[12-14] combined with education about stroke/TIA and the importance of medication adherence and support for lifestyle behaviour change.[15-18] Current NZ stroke guidelines recommend behavioural counselling for diabetes, diet, exercise and smoking cessation for long-term self-management of risk factors.[19] However, in NZ, management of TIA/minor stroke *remains inadequate*. [20] In addition, due to the transient nature of symptoms, *patients do not recognise TIA as a significant medical event* with long-term health implications. Resultant delays in seeking medical treatment, low adherence to healthy lifestyle and prescribed medications, lead to *preventable major secondary events*. [21-23]

---

### 3. EFFICACY OF LIFESTYLE INTERVENTIONS IN STROKE/TIA

A recent systematic review including 15 trials on lifestyle interventions for secondary prevention following TIA or ischemic stroke, with the majority based on educational material, lifestyle advice, or exercise training,[24] showed a significant lowering of systolic blood pressure, but no significant effect on cholesterol or mortality. The authors recommended that future trials test interventions with at least 8 contact points, using a theoretical framework,[25] including educational and behavioural interventions with at least a four-month follow-up, and considering factors such as self-efficacy to facilitate health behaviour change.[24] Well-designed health coaching interventions improve physical and mental health, and sustain changes in lifestyle-related behaviours in people with diabetes[26, 27] myocardial infarction,[28] and other chronic conditions. Resultant health behaviour changes have the potential to be long-lasting.[29]

---

### 4. MEASURING CARDIOVASCULAR RISK.

Testing an intervention that targets brain and heart health requires an evidence-based, relevant and reliable measure to determine its efficacy. Hypertension or high blood pressure is the most significant risk factor for stroke. The landmark INTERSTROKE study conducted in over twenty-six thousand participants in 32 countries showed that a history of hypertension increased the risk of stroke by 2.64-fold, and was the most significant risk factor for stroke. [30] Moreover the Global Burden of Diseases studies have shown that high systolic blood pressure is the leading risk factor contributing to the burden of stroke with 79.6 million disability adjusted life years lost (DALYs), which equated to 55% of DALYs. [31, 32]. A meta-analysis of 48 randomised trials evaluating the effects of blood pressure lowering in the risk of major CVD events (including stroke) found that a reduction of 5 mm Hg systolic blood pressure was associated with an 11% reduction in major cardiovascular events in people with previous cardiovascular disease.[33]

A recent study from Finland examined the association of the LS7 with the risk of stroke men without a history of stroke. In terms of absolute blood pressure, the study found that average blood pressures were  $138.2 \pm 16.6$  mm Hg in the poor,  $132.0 \pm 16.5$  mm Hg in the average and  $118.6 \pm 12.4$  mm Hg in the optimum categories of the LS7.[34] Thus, an improvement from poor to ideal blood pressures could reduce systolic blood pressure by up to 13 mm Hg. The Novel Approach to Cardiovascular Health By Optimizing Risk Management (ANCHOR) trial demonstrated a 4.5 mm Hg reduction in systolic blood pressure using a behaviour change intervention in people with an increased risk of CVD. [35] While the incidence of stroke and new vascular events would be ideal primary outcomes, this outcome would require long term follow-up and a prohibitively large sample size [18, 24, 36]. Blood pressure is also considered as a practical paradigm for preventing cardiovascular disease and improving total health. [33]

Given the increased risk of secondary events in this population, a 6 mm Hg difference in systolic blood pressure is plausible with an effective intervention.[37]

As well as improving blood pressure, a key secondary aim of the trial is to address multifactorial modifiable risk factors as a way to lower the risk of stroke and CVD. The INTERSTROKE study also found that overall there were ten potentially modifiable risk factors are collectively associated with about 90% of the population-attributable risk of stroke.[30] including lifestyle related risk factors such as physical activity, diet, and smoking. The Life's Simple 7 (LS7) was developed by the American Heart Association, (AHA), to predict ideal cardiovascular health using seven domains or metrics.[37-39] These are; blood pressure, cholesterol, glucose, body mass index, smoking, physical activity, and diet.[37] The LS7 is a simple scoring system to assess cardiovascular health with scores ranging from 0 to 14, with the overall LS7 score categorised as inadequate (0–4), average (5–9), or optimum (10–14) cardiovascular health (see Table 1). Inadequate and average scores on the LS7 have a high association with increased CVD/stroke risk and mortality.[38] Ideal levels of the Life's Simple 7 factors are defined as: non-smoker or quit >1 year ago; body mass index (BMI) of <25 kg/m^2; ≥150 min/week of moderate+vigorous physical activity; 4 to 5 components of a healthy diet pattern; untreated total cholesterol of <5.2 mmol/L; untreated blood pressure of <120/80 mm Hg; and untreated fasting glucose of <5.6 mmol/L. The Reasons for Geographic and Racial Differences in Stroke study (REGARDS) found that in 22,914 people with no previous history of CVD, an improvement by one category (from inadequate to average or average to optimum) or of the LS7 score was associated with a 25% lower risk of stroke, and that a 1-point higher LS7 score was associated with an 8% lower risk of stroke.[37] In the Atherosclerosis Risk in Communities (ARIC) study of 1277 individuals who experienced a MI, adverse outcomes were inversely related to mid-life LS7 scores using the LS7 scoring where two-points are given for each optimum domain.[40] A recent review suggested that “an integrated socio-behavioural and medical intervention to improve LS7 factors was a potent and likely cost-effective approach to cardiovascular and general health promotion and disease prevention”.[41]

## HEALTH AND WELLNESS COACHING.

Health and Wellness coaching (HWC) is a multidimensional psychological behaviour change intervention aimed at improving self-management of lifestyle behaviour and maintaining health and wellbeing.[42] HWC is a goal-oriented, theory based,[25] client-centred partnership that has produced positive effects on health and enhanced well-being of patients with chronic disease.[43-45] HWC is a widely accepted and established intervention in the community,[46] and is of particular relevance to stroke prevention as it can address multiple risk factors. HWC fosters ongoing self-directed learning,[43] delivers a cost-effective[47] intervention in person or by telephone, and by medical or non-medical personnel,

thus saving cost and increasing the scope of implementation. Individuals who receive HWC have increased perceived health status, improved medication adherence, and physical activity,[48, 49] with significantly improved health outcomes shown in patients following myocardial infarction.[50-52]

---

## 5. THEORETICAL FRAMEWORK FOR HWC

In the context of this study the health and wellness coaching intervention is aimed at behaviour change which improves and physical health as well as the mental wellbeing of participants. However, behaviour change is challenging, and influenced by of physical, psychological and psychosocial factors, which may change over time. Motivating individuals to change unfavourable health behaviours is a challenge for health professionals, but growing evidence suggests that involving people in their own decision-making results in more favourable outcomes.[53]

There are several theoretical models for health behaviour change that support the HWC intervention. These include the concept of self-efficacy [54] in the health belief model, which focuses on attitudes and beliefs as a way to explain behaviour for improving lifestyle changes. Fostering a sense of self-determination, self-responsibility and ownership enhances motivation, satisfaction and adherence to healthier lifestyle choices.[55]The transtheoretical model proposed by Prochaska suggests that health behaviour is an interaction of five stages of change, processes of change and self-efficacy.[56] In this model, it is suggested that individuals move through stages of change: pre-contemplation, contemplation, preparation, action, maintenance and termination. Change may occur at different rates for individuals, and they may even move back and forth between stages, before achieving the final stage of termination. Self-change is a product of individuals doing the right thing (processes) at the right time (stages).

The HWC intervention is underpinned by a combination of these theoretical models, as HWC also encompasses the whole person and their beliefs, but it also considers the dynamic interaction between the person and their environment and all the factors that influence them.

---

## 6. PREVIOUS EVIDENCE FOR HWC FOR STROKE PREVENTIONS

We have recently completed (publication underway) a phase III randomised controlled trial (RCT) using HWC (PREVENTS study, n=320) [57] for **primary** stroke prevention in those with moderate and high risk of CVD (prior stroke or TIA excluded).

The study showed a significant difference in the change in LS7 score in the HWC group between baseline (7.08 [2.03]) and 9- months (7.39 [2.00]) compared to controls (baseline 7.15 [2.20], 9-months 7.15 [2.39]) (p=0.044). Among LS7 domains, regression analyses adjusting for age, sex and ethnicity showed statistically

significant increases in scores (indicating a positive change) for blood pressure ( $p=0.005$ ), and cholesterol ( $p=0.04$ ). The absolute blood pressure increased in both groups, but the increase was greater in the control group (10.58mmHg) than the HWC group (4.36mmHg). Cholesterol, blood glucose and BMI values also showed greater decreases in the HWC group compared to controls. The trial also demonstrated high acceptability and feasibility of the HWC intervention, positive feedback from participants and low dropout.

## TRIAL DESIGN

The **Trial of an Individualised Intervention for the Prevention of Stroke (TIIPS)** is a phase III, prospective, open-label, single-blinded end-point randomised controlled trial of 360 participants. The participants will be recruited from Auckland based public hospitals, including outpatient TIA clinics. The recruitment of participants from the existing health system will maximise the uptake of the intervention.

### 7. SAMPLE SIZE CALCULATION AND POWER ANALYSIS:

[figure not shown]
360 participants are required to provide 85% power (two sided  $\alpha=0.05$ ) to detect at least a 6 mm Hg clinically significant difference in systolic BP (SBP) changes at 6 months from baseline, between the HWC and UC groups. This estimation assumes a 20% non-compliance/loss to follow-up. Based on our previous HWC trial (Prevents RCT on HWC for primary stroke prevention, publication in preparation) [57] data in NZ stroke patients ( $n=251$ , 9-month BP change in HWC patients is 4.4 mm Hg (SD:18) and in usual care patients is 10.6 mm HG (SD 22).

The sample size estimations used the proc power procedure of SAS – a statistical analysis software. Using the means of the SBP changes in the two groups and the pooled standard deviation (SD 20) from the previous HWC trial, the calculation indicates  $n=352$ . R software was also used for simulating changes in BP for the two groups and yielded a simulated type II error  $< 0.10$  (statistical power  $> 0.90$ ) when  $n=300$  (simulation of 1000 and 10000 times). We adopted the simulated results because it uses two different group standard deviations, and it is under the budget limit control. After adjusted 20% attrition rate, the proposed sample size is  $n=360$ . The power calculation is also informed by literature that a 5mmHg reduction in SPB is clinically meaningful and leads to a 11% reduction in the incidence of stroke.

The results of the trial will be reported according to the Consolidated Standards of Reporting Trials (CONSORT) statement as outlined in the below flowchart. If required, we will apply The CONSERVE 2021 Statement; Guidelines for Reporting Trial Protocols and Completed Trials Modified, in the case of the study being affected COVID-19 Pandemic and Other Extenuating Circumstances.

---

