### 32. POWER CALCULATION

The sample of 360 participants will provide a simulated 90% statistical power (two sided  $\alpha=0.05$ ,  $\beta=0.10$ ) to detect a clinically significant 6 mmHg (SD $\pm$ 20) difference in systolic blood pressure change at 6 months post-randomisation, assuming 20% non-compliance/loss to follow-up.

Based on our RIBURST data (a observational stroke risk study)[94] data in NZ general population (n=1265, with 0.07% incident stroke or TIA), the required sample size (n=360) will also provide 90% power (2-sided alpha) to detect 20% relative risk reduction in 5-year absolute risk of stroke. The estimated 5-year risk of stroke after TIA and minor stroke in NZ appeared to be greater than that in Europe,[4] likely due to greater risk of stroke in Māori and Pacific people constituting 20% of the NZ RIBURST Study population.

---

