### 34. INFERENCE ANALYSES

Intention to treat (ITT)[95] analyses and per protocol analysis will be used. To address the primary hypothesis ANCOVA will be used to compare the difference in systolic blood pressure at 6-months post randomisation between the HWC and usual care groups, accounting for baseline stratification factors: (age, gender and ethnicity), referral centres, geographical region and known influential clinical characteristics (e.g., comorbidities). To address the secondary hypotheses linear mixed effects (LME) repeated measures models will be used to investigate the differences in (1) adherence to medication (2) health-related quality of life (3) incidence of new vascular events including death (4) life satisfaction (5) cognition (6) mood) and (7) health service utilisation costs between the HWC and Usual care groups, and by ethnicity (sub-group analysis) at 6-months (plus

life-style and adherence at 1-year post-randomisation. These LMEs will model effect of time (baseline, 3-, 6- 9- and 12-months (medication adherence, lifestyle and awareness at only 12 months), post-randomisation whilst accounting for key demographic stratification factors known to confound with outcomes. Any data not collected within 6-weeks of the follow-up points will be classified as missing data. Baseline covariates of age, sex, most recent blood pressure measure and any additional variables predictive of outcome data will be included in the imputation model.[46] The reasons for missingness and the reasons will be recorded and accounted for. Sensitivity analyses will be conducted to test the assumptions of the model (including a complete case analysis in which only subjects with complete data are included). Familywise error control will be used to account for the multiplicity of tests. Inferences will be based on a 5% significance level and two-sided alternatives.

For the analysis of - CVD adverse outcomes (fatal and nonfatal stroke, TIA, myocardial infarction and heart failure, death attributable to CVD and all-cause mortality), we will use Kaplan-Meier life-test and estimate the hazard ratios (HR) and adjusted HR using time-to-event Cox regression analysis. Time to event analysis will include recurrent events and time-dependant variables where appropriate.

Competing risk method will also be applied to compare the CVD adverse outcomes between the two interventional groups, accounting for mortality outcome.

---

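### The stated 85% and 90% power do not follow from the protocol's own inputs: 360 randomised with 20% loss gives about 72% for 6 mm Hg at SD 20

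*Protocol*

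**What the plan says.** - Section 7 states that "360 participants are required to provide 85% power" (two-sided 5%) for a "6 mm Hg clinically significant difference in systolic BP (SBP) changes at 6 months from baseline", allowing for 20% non-compliance or loss to follow-up.
- It takes its inputs from an earlier coaching trial: "9-month BP change in HWC patients is 4.4 mm Hg (SD:18) and in usual care patients is 10.6 mm HG (SD 22", and a "pooled standard deviation (SD 20) from the previous HWC trial".
- It reports two calculations. SAS PROC POWER gave n=352. An R simulation with unequal SDs gave power above 0.90 at n=300. The simulation was preferred because it used separate SDs and fitted the budget.
- "After adjusted 20% attrition rate, the proposed sample size is" 360.
- Section 10 repeats 6 mm Hg and SD 20 as the design values.
- Section 32 states: "The sample of 360 participants will provide a simulated 90% statistical power", again for 6 mm Hg, SD 20, two-sided 5% and 20% loss.
- Section 34 confirms the test: "Inferences will be based on a 5% significance level and two-sided alternatives".
- Section 7 describes the planning data as coming from New Zealand stroke patients. Section 6 says that trial was in primary prevention, with "prior stroke or TIA excluded".

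**The concern.** One sample size with one set of inputs cannot have both 85% and 90% power. Section 7 also set aside an analytic result of 352 for a simulation that needed only 300, although the SDs used (18 and 22) average to almost exactly the SD of 20 in the analytic calculation. Changing from a common SD to these two SDs cannot reduce the required number or raise power to that extent. The final step from 300 to 360 looks like multiplication by 1.2, which does not leave 300 after 20% are lost.

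This is the justification for the primary endpoint. If the true power is well below what is stated, a non-significant result could be read as evidence that coaching does not work, when the trial had a substantial chance of missing the effect it was designed to find.

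**Working it through.** **Inputs, all from the protocol.** Difference 6 mm Hg (sections 7, 10, 32), or 10.6 − 4.4 = 6.2 mm Hg from the earlier trial (section 7). SD of change 20, or 18 and 22 by group (section 7). Two-sided 5% (sections 7, 32, 34). Randomisation 180 per arm (Randomisation section). Loss 20% (sections 7, 32).

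**Formula.** With n evaluable per arm, SE = √((SD₁² + SD₂²)/n) and power ≈ Φ(difference/SE − 1.96). The percentages below use the noncentral t, which differs from this by less than half a percentage point.

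**1. The plan's n=352.** With 176 per arm, SE = 20 × √(2/176) = 2.132 and 6/2.132 = 2.814. Power ≈ Φ(0.854) = 0.80. So 352 reproduces as the evaluable total for 80% power at 6 mm Hg and SD 20, before any loss. To retain 352 after 20% loss, 352/0.8 = 440 must be randomised. The evaluable totals for 85% and 90% are 402 and 470.

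**2. The simulation at n=300.** With 150 per arm and SDs 18 and 22, SE = √((324 + 484)/150) = 2.321 and 6.2/2.321 = 2.671. Power ≈ Φ(0.711) = 0.76. A simulation of 10,000 trials with these means and SDs also gave 0.76. The unequal SDs are equivalent to a common SD of √(808/2) = 20.1, so they cannot explain a result above 0.90. If 300 is read as per arm, power is 96%.

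**3. The allowance for loss.** 300 × 1.2 = 360, whereas 300/0.8 = 375. With 360 randomised, 360 × 0.8 = 288 remain, or 144 per arm.

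**4. Power of the trial as sized.** With 144 per arm, SE = 20 × √(2/144) = 2.357 and 6/2.357 = 2.546. Power ≈ Φ(0.586) = 0.72.

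| Evaluable total | 6.0 mm Hg, SD 20 | 6.2 mm Hg, SD 20 | 6.2 mm Hg, SDs 18/22 |
|---|---|---|---|
| 288 (360 less 20%) | 71.8% | 74.6% | 74.2% |
| 300 | 73.6% | 76.3% | 75.9% |
| 360 (no loss) | 81.0% | 83.5% | 83.1% |

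No two-sided cell reaches 85%. With 288 evaluable, the SD of change would have to be 17.0 for 85% power or 15.7 for 90%. The detectable differences at SD 20 are 6.6 mm Hg (80%), 7.1 (85%) and 7.7 (90%). For the 5 mm Hg that section 7 cites as clinically meaningful, power is 56%.

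**5. Where 85% and 360 might come from.** A one-sided 5% test with 6.2 mm Hg and SD 20 needs 300 evaluable for 85% power, and 300 × 1.2 = 360. This fits, but it contradicts the stated two-sided test and uses the wrong allowance for loss. The document does not show whether this was the route.

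**6. If the 20% is non-compliance instead of loss.** Assume that all 360 are followed and that one fifth of the coaching arm gains nothing. The expected difference is then 0.8 × 6 = 4.8 mm Hg, and power with 180 per arm is 62%.

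**The case against.** The strongest objection is that 72% describes an unadjusted comparison of changes, while section 34 plans an ANCOVA. If that model includes baseline systolic BP, the residual SD is 20 × √((1 + r)/2), where r is the correlation between baseline and 6-month values. For 6 mm Hg and 288 evaluable, power is then 88% (r = 0.3), 86% (0.4), 83% (0.5), 81% (0.6) and 79% (0.7). On that reading 85% is attainable. The point stands to the extent that 72% is conditional on no baseline adjustment. It does not support the text: the covariates listed for the ANCOVA do not name baseline systolic BP, no correlation is given, and the calculation is built on the SD of change. Nor does any correlation from 0.3 to 0.7 reach the 90% of section 32.

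Three smaller objections limit what can be said about causes:

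- Section 7 does not describe the model fitted in the simulation, so confusing a total with a per-arm number is a plausible explanation and no more.
- The 352 carries no stated target power. It is an 80% figure only if 6.0 was entered; with 6.2 it would give 82.6%.
- The dilution figure of 62% assumes that 6 mm Hg is the effect under full compliance. The earlier trial's means may already include non-compliers, so the figure is a scenario and not an estimate.

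The slip in the allowance for loss is also minor taken alone (73.6% against 71.8%). The description of the planning population is a labelling error, since the same sentence calls that trial primary prevention.

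**Conclusion.** The concern holds. The two power statements are incompatible, and neither follows from the stated inputs. With 360 randomised, 20% loss, 6 mm Hg, SD 20 and a two-sided 5% test, unadjusted power is about 72% (about 71–75% across the protocol's own choices of difference and SD). That overstates power by 13 points in section 7 and by 18 points in section 32. The simulation result at n=300 is not reproducible for 300 in total. These figures assume normally distributed changes, 1:1 evaluable arms, and planning values that carry over from a primary-prevention population. Adjustment for baseline systolic BP could bring power into the 80s, but the protocol neither states nor relies on it in its calculation.

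**What to change.** Use one reproducible calculation in sections 7 and 32, and keep section 10 consistent with it:

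- **Power:** replace both statements with 360 randomised, 288 evaluable after 20% loss, and about 72% power for 6 mm Hg (SD 20, two-sided 5%, unadjusted), or 80% for 6.6 mm Hg.
- **Baseline adjustment:** if the primary model will include baseline systolic BP, say so in section 34. Then quote the adjusted power with the assumed correlation and its source (88% to 81% for correlations of 0.3 to 0.6).
- **Simulation:** remove the claim, or restate it with the model, the meaning of n and the corrected result (about 76% for 300 in total, unadjusted).
- **n=352:** give its inputs and target power. At 6 mm Hg and SD 20 it is an evaluable total for 80% power.
- **Loss:** show it as division by 0.8, and say whether the 20% means missing outcomes, non-compliance or both.
- **Planning data:** describe the source as a primary-prevention trial.

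The cost is wording in three sections and a less favourable stated power. It needs no extra participants and no change to trial conduct.
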